11.5.3 Best Tumor Response

An informative analysis of best tumor response in the period from treatment initiation through the date of the last post TACE liver MRI, as determined by the Central Reviewers based on mRECIST criteria, will be summarized as the number and percentage of patients in each response category (complete response, partial response, stable disease, progression) for the ITT and Evaluable populations.

11.5.4 Resource Utilization

11.5.4.1 Length of stay (LOS) in hospital following each TACE procedure

This will be reported as the number of continuous 24 hour periods spent in the hospital following each protocol specified TACE procedure. An analysis of the average number of 24 hour periods the patient was hospitalized following TACE procedures will be performed. If the data is normally distributed, the treatment groups will be compared using a t-test. If the data is found to differ substantially from a normal distribution, non-parametric methods will be used to compare the treatment groups.

11.5.4.2 Number of unscheduled hospitalizations from date of first TACE procedure to last protocol specified post-TACE visit

This will be analyzed as a categorical variable with the following categories: 0, 1, 2 or more. Treatment groups will be compared using Fisher's exact test.

11.5.4.3 Length of stay of unscheduled hospitalizations

This will be reported as a number of 24 hour periods spent in hospital and summarized for only those patients reporting one or more unscheduled hospitalizations during the study specified treatment phase of the investigation. An analysis of the average number of 24 hour periods the patient was hospitalized during unscheduled hospitalizations will be performed. If there is

sufficient data, treatment comparisons will be performed. If the data is normally distributed, the treatment groups will be compared using a t-test. If the data is found to differ substantially from a normal distribution, non-parametric methods will be used to compare the treatment groups.

11.5.4.4 New or increased use of non-over-the-counter pain medications from date of first TACE procedure to last post-TACE visit

This will be analyzed as the proportion of patients reporting new or increased usage of non-over-the-counter pain medications during the protocol specified treatment phase of the investigation. Treatment groups will be compared using Fisher's exact test.

11.5.4.5 New or increased use of antibiotic medications from date of first TACE procedure to last post-TACE visit

This will be analyzed as the proportion of patients reporting new or increased usage of antibiotic medications during the study specified treatment phase of the investigation. Treatment groups will be compared using Fisher's exact test.

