 - iii. 20% decline from any value at screening
 2. Neutropenia
 3. Alopecia
 4. Hyperpigmentation
 5. Mucositis
- iii. Evaluate Resource Utilization as assessed by:
 1. Length of stay in hospital following each TACE procedure
 2. Number of unscheduled hospitalizations
 3. Length of stay of unscheduled hospitalizations
 4. New or increased use of non-OTC pain medications
 5. New or increased use of antibiotic medications
- iv. Evaluate overall adverse event rates between the treatment groups
- v. Evaluate objective response rates as determined by mRECIST criteria in the treated area (ORR-T)
 1. In this evaluation progression is defined as new/continued tumor growth in the treated area(s) of the liver or extrahepatic spread. New

tumor growth within an area of the liver not previously treated will not be considered progression.

c. Tertiary Objectives

1. Evaluate Time to Untreatable Progression defined as hepatocellular cancer for which further localized treatment by resection, percutaneous ablation, or embolization is not an option, or when there is extrahepatic spread of the cancer

Untreatable progression will be determined by the Central Reviewers during the study treatment and protocol-specified treatment follow up visits. After the final study TACE and associated assessments, untreatable progression will be determined by the treating physician during survival surveillance

2. Explore the relationship between pharmacokinetic (PK) data and patient outcomes including survival, tumor response, and adverse events

3. Inclusion Criteria

Patients must meet all of the following inclusion criteria in order to be entered into the study:

- a. Age 18 or older
- b. Patient has signed informed consent
- c. Patient must have a diagnosis of hepatocellular cancer confirmed by at least one of the following:
 - i. Histological confirmation
 - ii. Magnetic resonance imaging (MRI) result with early enhancement and delayed enhancement washout of at least one solid liver lesion > 1 cm. Patient must also have evidence of cirrhosis or have chronic hepatitis B.
 - iii. Contrast enhanced computed tomography (CT) with early enhancement and delayed enhancement washout of at least one solid liver lesion > 1cm. Patient must also have evidence of cirrhosis or have chronic hepatitis B.
- d. Patient must not be suitable for treatment by resection or percutaneous ablation at time of study entry.

Patients not suitable for ablation due to lesion location may be enrolled

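### Length of unscheduled stay is compared only among hospitalized patients, a subset formed after randomization, so this one resource-use component can favor the wrong arm

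*Combined protocol and SAP*

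**What the plan says.** Protocol section 2.b lists "Length of stay of unscheduled hospitalizations" as one of five resource-utilization measures under the secondary objectives. Section 11.5.4.3 sets out its analysis. The outcome is "summarized for only those patients reporting one or more unscheduled hospitalizations" in the treatment phase. The analyzed quantity follows: "An analysis of the average number of 24 hour periods the patient was hospitalized during unscheduled hospitalizations will be performed". The arms are then to be compared on one condition, that there is "sufficient data, treatment comparisons will be performed". What counts as sufficient is not defined, and no other population is named for the comparison.

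The neighboring section 11.5.4.2 handles the number of unscheduled hospitalizations, from first TACE to the last protocol-specified visit, differently: "This will be analyzed as a categorical variable with the following categories: 0, 1, 2 or more". The arms are compared by Fisher's exact test, and patients with no admission stay in the analysis.

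Section 11.3.2 makes the ITT population primary for efficacy analyses, and 11.5.4.3 falls under the efficacy heading. Section 11.1 calls any treatment comparison with a two-sided p-value of 0.05 or less statistically significant.

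**The concern.** Being admitted is an outcome of treatment, not a baseline characteristic. If the arms differ in who is admitted, comparing stays among the admitted compares two differently selected groups, and randomization no longer protects the result. A treatment that spares patients short admissions leaves only its long ones in the analysis and so appears to lengthen stay.

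The protocol's own background makes such a difference plausible. The section on drug-eluting chemoembolization cites a 30-patient randomized study with 20 grade 3 or 4 events on cTACE against 4 grade 3 and no grade 4 events on the study device. If fewer severe events mean fewer admissions, the admitted subsets will differ when the product works as the sponsor hopes. A distorted comparison could then be reported as significant under section 11.1. Requiring sufficient data does not help, because more admissions narrow the interval without making the subsets comparable.

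**Working it through.** The plan gives no figure to reproduce here: no admission rate, length of stay or power is stated for this outcome.

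**Input from the documents:** 255 randomized patients per arm (section 11.2).

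**Assumptions:** in cTACE, 15% of patients have one unscheduled stay of 2 days, 15% have one of 8 days, and 70% have none. One admission per patient is assumed, so it does not matter whether the average is taken per admission or per patient. hqTACE is assumed to do nothing but prevent some admissions.

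**Formulas.** With *s* the proportion having a short stay and *l* the proportion having a long stay:
- mean over all patients = 2*s* + 8*l*
- mean among the hospitalized = (2*s* + 8*l*) / (*s* + *l*)

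**Results:**

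| Arm and scenario | *s* | *l* | Hospitalized-only mean (days) | All-patient mean (days) |
|---|---|---|---|---|
| cTACE | 0.15 | 0.15 | 1.5 / 0.30 = 5.0 | 0.30 + 1.20 = 1.5 |
| hqTACE, half the short stays prevented | 0.075 | 0.15 | 1.35 / 0.225 = 6.0 | 0.15 + 1.20 = 1.35 |
| hqTACE, all short stays prevented | 0 | 0.15 | 1.2 / 0.15 = 8.0 | 1.2 |
| hqTACE, all long stays prevented | 0.15 | 0 | 0.30 / 0.15 = 2.0 | 0.30 |

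In the second and third rows hqTACE is better by construction. The all-patient mean shows it, and the hospitalized-only mean points the other way. In the last row both measures point the right way. With 255 per arm, the third-row comparison would rest on about 0.30 × 255 = 77 cTACE and 0.15 × 255 = 38 hqTACE patients.

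**Chance of a significant wrong result.** Trials with 255 per arm were simulated (1,500 per scenario) with skewed long stays. Control admission was 20% or 30%; short stays of about 2 days affected 5 to 15 percentage points of patients and were all prevented by hqTACE; long stays were about 5 or 8 days. hqTACE was declared significantly worse among the hospitalized in 17% to 84% of trials by t-test and 24% to 97% by Mann-Whitney test. The lowest figures belong to 5 points prevented. These rates hold only if treatment prevents short stays and leaves long ones alone.

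**Precision of the all-patient comparison** (all short stays prevented):
- cTACE variance = 0.15 × 4 + 0.15 × 64 − 1.5² = 7.95
- hqTACE variance = 0.15 × 64 − 1.2² = 8.16
- SE = √((7.95 + 8.16) / 255) = 0.25 days
- difference = 1.5 − 1.2 = 0.3 days; 95% CI 0.3 ± 1.96 × 0.251, or −0.19 to 0.79

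**What section 11.5.4.2 would show in the same example.** Collapsed to any admission against none, 77/255 against 38/255 gives a Fisher p-value of about 0.00005.

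**The case against.** The strongest reply is that section 11.5.4.3 does not stand alone. Section 11.5.4.2 keeps non-admitted patients and, in the example with every short stay prevented, would clearly show fewer hqTACE admissions. A careful reader who sees fewer admissions beside longer stays among those admitted could work out what happened. This stands in part. A reader might infer that the whole resource-use objective would point the wrong way. The documents do not support that: one of five components is affected. But 11.5.4.2 does not repair 11.5.4.3, and the plan has no rule for reading the two together.

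A second reply is that duration of an admission is naturally defined only for admitted patients, and that the plan states the restriction openly. That justifies describing it. It does not justify a between-arm test read as a treatment effect.

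A third reply is that the example is chosen. This also stands: with long stays prevented the direction is correct, so the claim is that the comparison can mislead, not that it will.

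A reader might also infer that choosing the test after seeing the data is a serious fault. Sections 11.5.4.1 and 11.5.4.3 do say "If the data is normally distributed, the treatment groups will be compared using a t-test", with unnamed non-parametric methods otherwise and no criterion for normality. In simulations with no treatment effect, however, a fixed Shapiro-Wilk rule kept type I error at 4.6% to 5.1%, and always taking the smaller of the t-test and Mann-Whitney p-values gave 5.8% to 6.7%. That is a missing detail with little numerical effect.

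**Conclusion.** The concern holds for the single comparison in section 11.5.4.3. It conditions on an event after randomization that treatment may affect, and it can reverse the direction of a real benefit. In the assumed example, an arm that is better by 0.15 to 0.3 days per patient appears worse by 1 to 3 days among the hospitalized. These sizes rest on admission rates and stays that the documents do not give, and on short rather than long stays being the ones prevented. Section 11.5.4.2 reduces the risk of misreading without removing it. Overall survival, objective response and the adverse-event analyses are not touched, so this is a worthwhile repair to one secondary component and not a threat to the trial's main conclusion.

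**What to change.** In section 11.5.4.3, make the between-arm comparison total unscheduled hospital days per patient, from first TACE to the last protocol-specified visit, with zero for patients not admitted. Use all treated patients, or all randomized patients with a stated start date for those never treated. Report the mean difference with a bootstrap or permutation interval.

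State how death and early discontinuation are handled. Both shorten the time in which days can accrue, so an arm with early deaths could look better; days per unit of time at risk would serve as a sensitivity analysis.

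Keep the hospitalized-only stay as description without a test, presented beside the 11.5.4.2 result. As a minor wording point, name the non-parametric test for section 11.5.4.1.

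The cost is plan text and code; admissions and lengths of stay are already planned outcomes. The downside is precision: with an SE of about 0.25 days in the example, the all-patient difference may be inconclusive, which is a further reason to read it together with 11.5.4.2.

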11.5.5 Objective Response Rate for Treated Area of the Liver

An analysis of objective response rate (ORR) will be performed based on the Central Reviewers' assessment of response in the treated areas of the liver only based on data from the protocol specified treatment phase of the investigation. The analysis of this outcome will employ similar methods as the overall analysis of objective response.

11.5.6 Time to Untreatable Progression

The Time to Untreatable Progression (TTUP) will be calculated from the date of the first study TACE procedure to the date of first documented untreatable progression, defined as hepatocellular carcinoma for which further localized treatment by resection, percutaneous ablation, or embolization is not an option, or when there is extrahepatic spread of the cancer. Patients who do not have documented untreatable progression will be censored in the TTUP analyses at the last date known to be progression-free. Tumor response/progression will be assessed by the Central Reviewers during the protocol specified treatment phase of the study and by the treating physician during long term follow up. Reasonable effort will be made to capture information on documented untreatable progression during the long term follow-up period. Patients in the ITT population who do not have at least one post baseline MRI will be censored at 4 weeks post first TACE cycle (which is the timing of the first scheduled post baseline MRI). The TTUP analysis will be performed on the final unblinded locked database at the end of the study.

Median time to TTUP will be calculated for both treatment groups in the ITT and Evaluable populations using the Kaplan-Meier (product-limit) method and corresponding 95% confidence

intervals will be generated. Median times will be compared between the treatment groups using the log-rank test.

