In an effort to assess the level of patient blinding, per FDA recommendation, patients will be asked the following question after they have completed their protocol specified embolizations: *“What treatment do you think you received?”* with response options of cTACE, hqTACE, or Unknown. This data is informative in nature and will not have any influence on the analyses of the study outcomes.

The study will be unblinded once all of the patients have received up to three study TACE cycles and follow up study procedures (protocol specified treatment phase of the investigation) and the database has been cleaned and locked. Unblinded survival data collection will continue until all patients have died or been lost to follow-up.

Treatment and Assessment

Study patients will be randomized to receive hqTACE or cTACE, with a target dose of $75\text{mg}/\text{m}^2$ of doxorubicin for each TACE cycle (maximum dose of 150mg of doxorubicin per TACE cycle). Up to a total of 3 TACE cycles will be administered to each patient within approximately a 6 month period from initial treatment, based on response as determined by Central Reviewers, using mRECIST. See Study Flow Charts, Appendix A.

Taking windows for second and third TACE cycles into account (8 weeks \pm 2 weeks from prior TACE cycle) and assessments (4 weeks \pm 1 week from last embolization in current cycle), and a 4 week (\pm 1 week) time between treatment of lobes of patients with bilobar disease, the assessment of objective response rate for patients with unilobar disease will be 15-25 weeks and 24-40 weeks for patients with bilobar HCC.

Patients whose response to treatment during the study makes them eligible for potentially curative therapies such as transplant, resection or percutaneous ablation will be offered those treatments, as appropriate in the decision of the treating physician. They will be discontinued from the treatment portion of the study and followed for survival per protocol.

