7.9 Survival follow -up

Patients will be followed from date of first embolization of the first cycle until a date of death is obtained or the patient is lost to follow up. Survival contacts will be attempted every 3 months after completion of final protocol-specified study visit. Contacts may be by visit, telephone, email, or written response, and may be obtained from the patient, medical records, or care givers/family members. Patients may undergo further treatment after the study-specified TACE treatments at the discretion of their physicians, including but not limited to transplant, resection, percutaneous ethanol injection (PEI), radiofrequency ablation (RFA), additional

embolizations, sorafenib or other treatments, including other investigational methods. Patients who have additional embolizations after the three protocol-defined TACE cycles must have the same type of embolization (cTACE or hqTACE) they received during the study. It would be unethical to deny these patients further treatment which might provide benefit, but any and all of the above could affect long term survival and be confounds in the analysis and interpretation of this study data. For this reason treatments and outcomes after the final study TACE will be documented, to the extent possible, during the survival follow-up period, but will not be considered safety or efficacy outcomes in this study, except time to untreatable progression (TTUP). Survival and TTUP will be the only outcomes evaluated after completion of the protocol specified treatment phase of the investigation.

7. Withdrawal of Patients

Patients will be informed that they have the right to withdraw from the study at any time for any reason, without prejudice to their medical care. The investigator also has the right to withdraw patients from the study for any of the following reasons:

- Adverse events, including cardiac ejection fraction <50%
- Progression to extrahepatic disease
- Refusal of treatment
- Patient request
- Inability to complete study procedures
- Lost to follow up
- Non compliance with study requirements

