11.2 Sample Size Calculations

The sample size calculation for the primary efficacy analysis of the comparison of median overall survival between the two groups is based on the assumption of a 16 month median survival in the cTACE group and a 24 month median survival in the hqTACE group. A sample size of 196 patients per treatment group will have 85% power to detect this difference in median survival (Hazard ratio= 1.500) based on a 2-sided Type I error rate of 5%. Assuming a 30% non-evaluable rate, a total of 255 patients will be enrolled and randomized into each treatment group.

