APPENDIX A

1. Study Flowchart: Unilobar Disease

[figure not shown]
2. Study Flowchart: Bilobar Disease

3. Schedule of Study Events

1. Study Flowchart: Patients with Unilobar Disease

2. Study Flowchart: Patients with Bilobar Disease

3. Schedule of Procedures						
	Screening (within 4 weeks +/- 1 week of first TACE)	TACE Treatment Period ¹			Post-final TACE Study Visit ²	Survival Follow- up ³
	Visit -1	Tx Visit 1	Tx Visit 2	Tx Visit 3	Visit 4	
Informed Consent	X					
Eligibility criteria assessment	X					
Demographics	X					
Baseline HCC Review ⁴	X					
Medical History	X					
Concurrent Medical Conditions	X					
Physical Examination ⁵	X				X	
Vital signs	X				X	
Serum Pregnancy test	X					
Hematology / Serum Chemistry ⁶	X	X	X	X	X	
Urinalysis	X	X	X	X	X	
Tumor Evaluations (MRI) ⁶	X	X	X	X		
Alpha-feto protein (AFP) ⁶	X	X	X	X	X	
12-lead ECG	X				X	
Cardiac Ejection Fraction ⁷	X		X		X	
Randomization ⁸						
Embolization procedures (TACE)		X	X	X		
Resource Utilization		X	X	X		
Adverse Events		From randomization to protocol defined follow- up period				
Concomitant Medications		X				
Protocol deviations/violations		X				
Survival status						X
Additional cancer treatments						X
Pharmacokinetic Sampling ⁹		X				

¹ First TACE Cycle must be begin within 4 weeks (± 1 week) of baseline MRI and labs. If the patient has bilobar disease, the embolization of the first lobe must be within 4 weeks (± 1 week) of baseline MRI and labs and the second lobe must undergo embolization within 4 weeks (± 1 week) of the first lobe.

A second TACE cycle is required for all patients, unless the investigator deems further treatment unsafe for the patient. The second TACE cycle must be within 8 weeks (± 2 weeks) of first TACE cycle. If the patient has bilobar disease, the first lobe of the second TACE cycle must undergo chemoembolization within 8 weeks (± 2 weeks) of the second lobe in the first TACE cycle, and the second lobe of the second TACE cycle must undergo chemoembolization within 4 weeks (± 1 week) of first lobe in the second TACE cycle.

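### No scheduled item records dated untreatable-progression status after the last study MRI; if event-free dates are not collected, the TTUP curves fall too fast, and under partial or unequal recording the direction of bias is unknown

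*Combined protocol and SAP*

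**What the plan says.** Tertiary objective 1 (section 2c) passes the determination from the Central Reviewers to the site once study treatment ends: "untreatable progression will be determined by the treating physician during survival surveillance". Section 7.9 names survival and TTUP as the only outcomes evaluated after the treatment phase.

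Section 11.5.6 promises "Reasonable effort will be made to capture information on documented untreatable progression during the long term follow-up period". Patients without a documented event are censored at the latest date on which they were known to be free of progression. The section does not say which assessment provides that date after the last MRI, how often, or on what evidence.

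The Survival Follow-up column of the Appendix A schedule has two marked rows: survival status and "Additional cancer treatments". MRI is marked only up to the third treatment visit. On the 3-monthly contacts, section 7.9 says: "Contacts may be by visit, telephone, email, or written response, and may be obtained from the patient, medical records, or care givers/family members".

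On timing, section 11.5.6 says "The TTUP analysis will be performed on the final unblinded locked database at the end of the study", and section 6 says "Unblinded survival data collection will continue until all patients have died or been lost to follow-up". Footnote 3 of the schedule instead gives survival follow-up of 2 years from the first embolization.

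**The concern.** A Kaplan-Meier estimate needs two kinds of date: when events happened, and how long each event-free patient was known to be event-free. After the last MRI the plan makes an explicit effort for the first kind and schedules nothing for the second. If no event-free date is collected, patients without an event drop out of the risk set at about their last MRI. Patients who later have a documented event stay in it until that event. From then on the risk set holds only patients who are going to fail, so the curve falls too steeply.

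At stake are the TTUP medians, the log-rank comparison and any hazard ratio quoted with them. Treating radiologists know the treatment, and follow-up data are collected unblinded, so the completeness of event-free dates could also differ between arms.

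**Working it through.** **The plan's own figure.** The documents give no power, sample size or event count for TTUP. The nearest figure is for overall survival: "16 month median survival in the cTACE group and a 24 month median survival in the hqTACE group", hazard ratio 1.5, two-sided 5%, 85% power. Schoenfeld: 4 × (1.960 + 1.036)² / (ln 1.5)² = 4 × 8.978 / 0.1644 = 218.4, against 218 deaths in section 11.5.1. It reproduces, but says nothing about TTUP.

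**Last MRI.** Unilobar: cycles at weeks 0, 8 and 16, MRI 4 weeks later = week 20. Bilobar: embolizations at weeks 0, 4, 12, 16, 24 and 28, MRI 4 weeks later = week 32. Midpoint: week 26, about 6 months.

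**Assumptions.** Exponential TTUP with true medians of 12 and 20 months (not from the documents); no event-free date after the last MRI at time m; each later event captured with the same probability.

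**By hand, follow-up fixed at F.** After m only patients with a captured event by F remain in the risk set, so for m < t ≤ F

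S*(t) = S(m) × [S(t) − S(F)] / [S(m) − S(F)].

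The capture probability cancels. With m = 6 and F = 24 (footnote 3), set S*(t) = 0.5:
- True median 12: S(6) = 0.707, S(24) = 0.250. S(t) = 0.250 + (0.5/0.707) × 0.457 = 0.573, so t = 12 × log2(1/0.573) = 9.6 months.
- True median 20: S(6) = 0.812, S(24) = 0.435. S(t) = 0.435 + (0.5/0.812) × 0.377 = 0.667, so t = 20 × log2(1/0.667) = 11.7 months.

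**By hand, complete follow-up with independent deaths at an assumed median of 24 months.** After m, events that precede death arrive at the combined rate, so t = 6 + (1 − 6/M) / (1/M + 1/24) for true median M:
- M = 12: 6 + 0.5/0.125 = 10.0 months.
- M = 20: 6 + 0.7/0.0917 = 13.6 months.

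**Simulation** (255 per arm, half bilobar, MRI at week 20 or 32, no event-free dates after it, 30-100% of later events captured):

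| Follow-up | True 12 | True 16 | True 20 |
|---|---|---|---|
| 9-33 months | about 9 | about 10 | about 11 |
| 24-48 months | about 11 | about 13 | about 14 |
| Complete, no deaths | 12 | 16 | 20 |
| Complete, deaths at median 24 | about 10 | about 12 | about 14 |

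**Treatment contrast, equal recording** (255 per arm; medians 12 v 18, true hazard ratio 0.667; last MRI uniform over 3.5-9 months; 24-month accrual plus 24 months; 70% of later events captured). With no later event-free dates, the medians read 10.9 v 13.8, the hazard ratio 0.77, and log-rank power is 66%. If the same 70% of patients have both events and event-free dates recorded, the hazard ratio is 0.67 and power 95%. With no true difference, the hazard ratio stays near 1.0 and the log-rank error near 5%.

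**Partial recording** (event-free status recorded at 25% of contacts, 9-33 months, true 12/16/20):
- 100% of events captured: 10.5/13.3/15.6, too short.
- 70% captured: about 11.7/14.9/18.0.
- 30% captured: about 16/22/25, too long.

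**Unequal recording** (later event-free dates for 20% of non-events in one arm and 60% in the other, control median 12, 70% capture). With no true difference the hazard ratio is 0.89 or 1.12, depending on which arm is better documented, and the false-positive rate is 17-20%. A true 0.667 becomes 0.63 or 0.84.

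**The case against.** The strongest reply is that the plan leaves the event-free date undefined but does not exclude it. Section 11.5.6 has the treating physician assess progression in long-term follow-up. Section 11.1 keeps follow-up data flowing into the database for TTUP. Section 7.9 allows contact by visit and use of medical records. A recorded later resection, ablation or embolization is indirect evidence that local treatment was still an option on that date. The case report form is not in the documents. All of this stands, and it is why the conclusion is conditional. It does not remove the gap: such evidence is unsystematic, and it is missing for patients who need no further treatment.

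Four stronger readings might be inferred, and the documents do not support them:
- That event-free time goes unrecorded. They show only that no scheduled item records it.
- That arm differences always shrink. That needs equal recording; the unequal case above can also widen them.
- That a true 8-month gap in medians will show as about 2. That is the 9-33 month case with no event-free dates. With complete follow-up and deaths at a 24-month median the gap is nearer 4 months, and without deaths the bias vanishes.
- That TTUP must wait for the last death. At a 24-month median the expected last death among 255 patients is 6.12 × (24/ln 2) = 6.12 × 34.6 = 212 months. But section 11.5.6 does not define the end of the study, and footnote 3 limits follow-up to 2 years.

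**Conclusion.** The point holds as a conditional one. After the last study MRI no scheduled item produces dated untreatable-progression status, while the analysis rule depends on it. If the schedule is followed as written and event-free dates are not collected, true TTUP medians of 12 and 20 months read about 9 and 11 (9-33 months of follow-up) or about 10 and 14 (complete follow-up, deaths at an assumed 24-month median). With equal recording in both arms the contrast is diluted. With partial or unequal recording, neither the size nor the direction of the bias can be known.

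These sizes rest on exponential times, assumed medians, deaths independent of progression, and event capture unrelated to timing. TTUP is a tertiary objective with no power claim, and the overall survival analysis is unaffected. This is a cheap improvement to make prospectively, because missing event-free dates cannot be reliably rebuilt later.

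**What to change.** 1. Add a row to the Survival Follow-up column of Appendix A, and a matching sentence to section 7.9: at each 3-month contact record untreatable progression (yes, no or unknown), its date and its basis, taken from the treating physician or the medical record.
2. In section 11.5.6, censor event-free patients at the last contact with a recorded 'no', by the same rule in both arms.
3. Reconcile the 2-year follow-up in Appendix A footnote 3 with follow-up until death or loss in sections 6 and 7.9, and state the TTUP data cut-off. Using the primary overall survival cut-off is an option, not a correction; TTUP would then be analysed with fewer events than at a later cut-off.

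The cost is one case report form line at contacts already planned, plus some analysis-plan wording. The downside is that sites must check the treating physician's record at every contact.
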